10.7 INTERIM MONITORING GUIDELINES

The objectives of interim monitoring are to (1) monitor for safety, (2) track participant accrual rates, and (3) monitor the primary and secondary outcomes for early evidence of efficacy, harm or futility. To accomplish this, summaries of data quality, accrual, adherence, distribution of baseline factors, toxicity, study endpoints and other analyses as requested will be prepared for review by the Data Safety Monitoring Committee (DSMB).

The primary outcome of the trial, rate of first event requiring any ICD therapy, is the basis for formal interim analysis plan that follows. One interim analysis and one final analysis are planned for this trial, for a total of 2 analyses. These analyses will be performed when 0.5 and 1.0 fraction of the total number of events will have been observed. Since this study will have a target number of events of 70, we will have approximately 35 events observed between each analysis time.

We will use an alpha-spending O'Brien-Fleming sequential procedure as a guideline for decision making. At the interim analysis the value of the test statistic will be compared with the alpha spending function critical values. The two alpha values will be set at 0.0054 at the interim analysis and 0.0492 at the final analysis, which equate to critical values of 2.782 and 1.967 respectively. This monitoring plan maintains the overall type I error at 0.05, given one interim analysis.

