9.2 POST-PROCEDURE

9.2.1 POST-PROCEDURE FOLLOW UP

- All patients will be monitored to verify vascular hemostasis prior to discharge from the hospital.
- All patients will receive either oral aspirin (81-325 mg QD) or clopidogrel (75 mg QD) or warfarin or one of the NOACs (dabigatran, rivaroxaban, Apixaban) for at least 1 week upon discharge.
- Medication and adverse event review will be performed prior to discharge.
- Complications including vascular, stroke, heart failure etc., and presence of ventricular arrhythmias will be documented.
- ICD programming: (see below section 9.2.3)
- The total number of episodes of VT, ATP, and Shocks will be documented at all visits.
- The follow-up includes:
 - 1 Month (\pm 14 days):
 - History and Physical
 - ICD interrogation
 - Office BP measurements (x2) including orthostatics
 - Review of Medications and Adverse events
 - 6 Months (\pm 30 days):
 - History and Physical
 - ICD interrogation
 - Office BP measurements (x2) including orthostatics
 - Lab tests (CBC, Electrolytes, BUN/Cr)
 - BNP Level

- Review of Medications and Adverse Events
 - Repeat Renal Ultrasound or MR/CT Angiography
- 12 Months (\pm 30 days):
 - History and Physical
 - ICD interrogation
 - EKG
 - Office BP measurements (x2) including orthostatics
 - Lab tests (CBC, Electrolytes, BUN/Cr)
 - Blood for Renal Hormones (OPTIONAL)
 - BNP Level
 - Review of Medications and Adverse Events
 - Repeat TTE
- 18 Months (\pm 30 days):
 - History and Physical
 - ICD interrogation
 - Office BP measurements (x2) including orthostatics
 - Review of Medications and Adverse Events
- 24 Months (\pm 30 days):
 - History and Physical
 - ICD interrogation
 - Office BP measurements (x2) including orthostatics
 - Lab tests (CBC, Electrolytes, BUN/Cr)
 - BNP Level
 - Review of Medications and Adverse Events
- 36 Months (\pm 30 days):
 - History and Physical
 - ICD interrogation
 - Office BP measurements (x2) including orthostatics
 - Lab tests (CBC, Electrolytes, BUN/Cr)
 - BNP Level
 - Review of Medications and Adverse Events

Patients will be followed for a maximum of 36 months until the final patient reaches the 18 month follow-up time point. Once the final patient reaches the 18 month follow-up time point, all follow-ups will cease.

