10.6 POWER AND SAMPLE SIZE

Power for this study was determined based on the following operating characteristics: (a) two sided type I error fixed at 0.0492, assuming one interim analysis, (b) 85% power, (c) minimum follow-up of 18 months, (d) 18-months event rate in the ICD alone group of 19% (e) expected 18-month relative rate reduction in the ICD + RSDN group of $\geq 40\%$, accrual period of 48 months and non-uniform accrual.

Under the above assumptions it is estimated that 70 events (or 462 patients) will be required to detect a relative decrease in the relative event rate reduction requiring any ICD therapy $\geq 40\%$ in the ICD + RSDN compared to the ICD alone group (19% vs. 11.4%) (Lachin, 1981).

Lost to Follow Up: The term "lost to follow-up" is used to define an individual who has withdrawn consent to be in the study or who can no longer be located or assessed. Such individuals represent those for whom primary outcome assessment is no longer possible. Since the primary outcome will be assessed by interrogating the ICD and since patients come back to

the hospital for regular check we do not anticipate a high rate of lost to follow-up. The estimated sample size accounts for 5% attrition due to withdrawal of consent.

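### Section 10.7 times the final analysis by event count, but 9.2.1, 10.6 and 10.8 use 18-month rules; nothing says which sets the data cut-off

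*Combined protocol and SAP*

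**What the plan says.** Four sections of the combined protocol and SAP bear on when the primary hypothesis is finally tested.

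- **10.7 (interim monitoring)** is event-driven: "These analyses will be performed when 0.5 and 1.0 fraction of the total number of events will have been observed". The target is 70, so the looks fall at about 35 and 70 events, with fixed critical values of 2.782 and 1.967.
- **9.2.1 (follow-up)** is calendar-driven. Each patient is followed for up to 36 months, and "Once the final patient reaches the 18 month follow-up time point, all follow-ups will cease".
- **10.6 (power)** assumes "minimum follow-up of 18 months" and an "accrual period of 48 months and non-uniform accrual". The last patient's 18-month visit therefore falls at about month 48 + 18 = 66. The accrual pattern is not given.
- **10.8 (analysis)** censors patients who are event-free when an 18-month follow-up period ends.

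The documents do not say which rule fixes the final data cut-off. They do not say what happens if 70 events arrive before everyone has 18 months, or if follow-up closes with fewer than 70. They also leave open whether an event after a patient's month 18 counts toward the 70.

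**The concern.** An event count and a closing date lead to the same analysis only if events arrive at exactly the planned pooled rate. Otherwise the statistician must choose one, and the choice fixes the data cut, the power, and the fraction of information available at the interim look. If 10.7 is followed to the letter, the test may be run on a data set that does not meet the follow-up minimum in 10.6 and has fewer events than the trial would collect anyway. If 9.2.1 is followed, the 35-event look is not necessarily a half-information look, and the fixed pair of critical values was set for one half. A choice left open until data have accumulated is also harder to defend than one written down beforehand.

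**Working it through.** **Inputs.** From 10.6: 18-month event rates of 19% and 11.4%, 462 patients (231 per arm), 48 months of accrual, two-sided alpha 0.0492, 85% power. From 9.2.1: at most 36 months per patient and close at month 66. Assumptions: exponential event times, no loss unless stated, and accrual either uniform or rising linearly, because the plan says only that it is non-uniform.

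**1. The plan's 70.** 462 × (0.19 + 0.114)/2 = 70.2. So 70 is the number of events expected if every patient is counted for exactly 18 months. It is not the number needed for 85% power:

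- HR = ln(1 − 0.114)/ln(1 − 0.19) = 0.574, so ln HR = −0.554.
- Schoenfeld: 4 × (1.967 + 1.036)² / 0.554² ≈ 117.4, rounded up to 118 events.

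**2. Power by event count.** Power = Φ(0.554 × √D/2 − 1.967).

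| Events D | Power |
|---|---|
| 64 | 60% |
| 70 | 64% |
| 110 | 83% |
| 118 | 85% |

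**3. Events counted to 36 months per patient.** The hazards are −ln(0.81)/18 = 0.0117 and −ln(0.886)/18 = 0.0067 per month. Expected events by calendar month t are the sum over arms of 231 × the average, over entry times e, of 1 − exp(−λ × min(36, t − e)).

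| Accrual | 70th event expected | Events at month 66 |
|---|---|---|
| Uniform | month 43.0 | 118 |
| Linear ramp | month 50.9 | 110 |

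At month 43 under uniform accrual, 462 × 43/48 = 414 patients are enrolled, and 462 × 25/48 = 241 of them were randomised at least 18 months earlier. Under the ramp, at month 50.9, that number is 462 × (32.9/48)² = 217. The 18-month minimum is unmet in both cases. With 5% attrition, the close yields about 106-113 events (power about 81-84%).

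**4. Patients censored at 18 months.** The expected total at month 66 is 70.2 under any accrual pattern. The count is the sum of two binomials, (231, 0.19) and (231, 0.114).

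- P(fewer than 70) = 47%.
- The mean count among trials that miss is about 64, and P(fewer than 60) = 8%.
- With 5% attrition, the chance of missing 70 is 55-57% if losses are spread over follow-up, and 66% if those patients contribute nothing.

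**5. Does a corrected target settle it?** Take a target of 118, counting to 36 months, with uniform accrual:

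- 25% vs 15%: reached at month 51.
- 19% in both arms: reached at month 53.
- 14% vs 8.4%: never reached, with 89 events at the close.

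The event rule and the close still diverge whenever the rate differs from plan.

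**6. Interim boundary.** With about 118 final events, a 35-event look has 35/118 ≈ 0.30 of the information. The O'Brien-Fleming-type spending function 2[1 − Φ(1.96/√t)] gives 0.00035 at t = 0.30, so |z| = 3.58, against the fixed 2.782. Using the fixed pair 2.782/1.967 throughout, the joint two-sided error is 0.0526 at t = 0.30 and 0.0513 at t = 0.5.

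**The case against.** The case against a stronger reading is substantial, and much of it stands.

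- *A reader might infer two competing analysis triggers.* Section 9.2.1 ends follow-up visits and does not mention the analysis, and 10.6 lists 18 months as a power assumption. Only 10.7 times an analysis. Under the censoring in 10.8, the target and the close even coincide in expectation (70.2 events). The rules are unreconciled, not contradictory.
- *A reader might infer that the test will be run before accrual ends.* At design rates that requires counting events beyond 18 months and accrual that is not strongly back-loaded. The chance is 95% with uniform accrual, 80% with a 12-month ramp followed by a constant rate, and 10% with a linear ramp. With 18-month censoring, only about 57 events (uniform) or 48 (linear ramp) are expected by month 48.
- *A reader might combine early testing with never reaching 70.* At design rates these belong to different readings of the countable-event window. The miss is usually small: 60% power at 64 events against 64% at 70.
- *A reader might call the final analysis the only confirmatory test.* Section 10.7 also plans a formal efficacy look at the primary outcome, with alpha 0.0054.
- *A reader might infer serious type I error inflation or cut-off shopping by people who have seen results.* The mistimed look adds about 0.0013 to the joint error, and 10.7 calls the procedure a guideline. No passage shows that those choosing the cut-off would see unblinded results, and 9.3.3 limits the principal investigator to open sessions.

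It is also fair to say that 64% power at 70 events comes from a target that is too low, which is a defect in its own right. But step 5 shows that correcting the target leaves the timing open, and none of these objections supplies the missing rule.

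**Conclusion.** The point holds in a limited form: the plan does not define the final data cut-off uniquely. On the 36-month reading, following 10.7 to the letter means testing about 15 to 23 months before the month-66 close (66 − 51 and 66 − 43), with 64% power where waiting would give about 83-85%. On the 18-month reading, the specified trigger fails in about 47% of trials, or more with attrition, mostly by a small margin. The efficacy threshold at a 35-event look could be much more lenient than the named method allows at that information, although the effect on overall error is small. These sizes rest on exponential times, the plan's rates and assumed accrual shapes. The absence of a precedence or fallback rule rests on the text alone.

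**What to change.** 1. In 10.7, set the final analysis at the common closing date of 9.2.1, the last randomised patient's 18-month visit.
2. In 10.8, state whether events after a patient's month 18 count, and align the event target in 10.6 and 10.7 with that choice. If they count, about 110-118 events are expected. If they do not, about 70 are expected, and the stated 85% power must be revisited, because 70 events give 64%.
3. Set the interim look at half the resulting expected final count: about 55-59 events or about 35, depending on item 2.
4. Compute both critical values from the named spending function at the information actually observed, in place of the fixed pair 2.782/1.967.

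If events after month 18 count, this costs SAP wording only and no extra patients or visits. The downside is that the final event count is no longer fixed in advance, so power varies with the event rate (89 events at 14% vs 8.4%, for example). An event target combined with an 18-month minimum and a calendar fallback would also be defensible; what matters is that one rule is written down before accumulating data can influence it.

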the interaction between the indicator for treatment group and log (t) in a Cox proportional hazards regression model that also includes the main effect for the randomization group. The final analysis will be based on a two tailed 0.0492 level test.

Analysis of Secondary End-points: All continuous variables will be analyzed using mixed effects models (Bagiella et al. 2000; Diggle et al. 1994; Laird and Ware 1982). Log-transformations will be used, if necessary to normalize the variables or stabilize the variance. For binary and discrete outcomes we will use generalized estimating equations (GEE) (Liang and Zeger 1986; Miller et al. 1993; Zeger and Liang 1986) to fit logistic or log-linear models that account for the dependency of the repeated measures.

Missing Data: For participants who withdraw consent to participate we will use all the information available up to the time of withdrawal. For the purpose of the primary analysis these patients will be censored at the time of withdrawal if they have not experienced the primary event. For all other variables, if the data are missing at random (MAR), that is, the probability of being missing depends only on observed values (Little and Rubin 1987), then likelihood-based methods such as mixed-effects models will be used for analysis without bias. If the fraction of missing data is small we expect that even non-ignorability can have only little effect on the final estimates. If the extent of missingness is large compared to the effect size, we will use the multiple imputation procedure proposed by Rubin (1997) and Little (1996).

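### The critical values 2.782 and 1.967 give an overall two-sided type I error of about 0.0513, not the 0.05 the plan claims

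*Combined protocol and SAP*

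**What the plan says.** Section 10.7 (Interim Monitoring Guidelines) sets out an O'Brien-Fleming alpha-spending procedure for the primary outcome.

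- Number of looks: "One interim analysis and one final analysis are planned for this trial, for a total of 2 analyses".
- Timing: "These analyses will be performed when 0.5 and 1.0 fraction of the total number of events will have been observed". With 70 events as the target, the interim falls at about 35.
- Levels: "The two alpha values will be set at 0.0054 at the interim analysis and 0.0492 at the final analysis". The matching z thresholds are given as 2.782 for the interim and 1.967 for the final look.
- Claim: "This monitoring plan maintains the overall type I error at 0.05, given one interim analysis".

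The final level recurs in two other places. Section 10.6 bases the power on a "two sided type I error fixed at 0.0492, assuming one interim analysis". Section 10.8 says "The final analysis will be based on a two tailed 0.0492 level test".

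Futility is listed among the aims of monitoring, but no futility boundary is given. The spending function is not written out, and nothing is said about recalculating the critical values if the interim look misses the 0.5 fraction.

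**The concern.** For two looks at fixed fractions, the overall error follows from the two critical values alone, so the claim can be checked directly. The stated pair has the O'Brien-Fleming shape, since 1.967 × √2 = 2.782, but 1.967 is smaller than the constant that shape needs for an overall 0.05. Against the familiar tabulated versions, the interim value lies near the classical boundary and the final value near the spending-function boundary. The two together match neither.

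These values decide whether the trial can claim efficacy. If they are too lenient, some results would be declared significant that a rule truly holding 0.05 would not allow, either at the interim (z between 2.782 and a stricter boundary) or at the end (p just under 0.0492).

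**Working it through.** **Inputs, all from section 10.7:** looks at t = 0.5 and 1.0; critical values c1 = 2.782 and c2 = 1.967; two-sided levels 0.0054 and 0.0492; claimed overall error 0.05. Sections 10.6 and 10.8 confirm that the test is two-sided.

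**Step 1. The plan's conversion from level to critical value.** The two-sided level 0.0054 gives z = 2.7822, and 0.0492 gives z = 1.9669. Both agree with the plan, so the conversion is not the source of the problem.

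**Step 2. Overall error of the stated pair.** Under the null, the interim and final statistics are, in large samples, bivariate standard normal with correlation √(0.5/1.0) = 0.7071. Then

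overall α = 1 − P(|Z1| < c1 and |Z2| < c2).

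| Calculation | Overall two-sided error |
|---|---|
| c1 = 2.782, c2 = 1.967, numerical integration | 0.05128 |
| Exact levels 0.0054 and 0.0492 in place of rounded z | 0.05129 |
| Simulation, 20 million pairs | 0.05131 (SE 0.00005) |
| Twice the one-sided error, 2 × 0.02564 | 0.0513 |

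The interim look spends 0.0054, and the final look adds 0.0513 − 0.0054 = 0.0459. Moving both critical values to the limits of their rounding changes the total only between 0.0512 and 0.0513.

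**Step 3. Does any standard O'Brien-Fleming version give this pair at t = 0.5?**

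- *Classical boundary.* Solve overall α(c√2, c) = 0.05 for c. The result is c = 1.9774.
- *O'Brien-Fleming-type spending, 0.025 per side.* The two-sided amount spent at t = 0.5 is 4[1 − Φ(2.2414/√0.5)] = 0.00305. The final value is then solved so that the total is 0.05.
- *Same function applied to the two-sided 0.05 directly.* The amount spent is 2[1 − Φ(1.960/√0.5)] = 0.00557, and the final value is solved as before.

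| Version | Interim z (level) | Final z (level) |
|---|---|---|
| Plan | 2.782 (0.0054) | 1.967 (0.0492) |
| Classical | 2.797 (0.0052) | 1.977 (0.0480) |
| Spending, 0.025 per side | 2.963 (0.0031) | 1.969 (0.0490) |
| Spending, two-sided form | 2.772 (0.0056) | 1.979 (0.0478) |

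None reproduces the stated pair.

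**Step 4. What would make the pair consistent?** Keeping 2.782 at the interim requires 1.979 (0.0479) at the end. Keeping 1.967 at the end requires 3.009 (0.0026) at the interim. Keeping both requires the interim to fall at about 0.70 of the events rather than 0.5.

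**Step 5. Sensitivity to the timing of the interim, with both values held fixed.**

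| Event fraction at interim | Overall error |
|---|---|
| 0.30 | 0.0526 |
| 0.40 | 0.0519 |
| 0.50 | 0.0513 |
| 0.60 | 0.0506 |
| 0.70 | 0.0500 |

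An early look makes the excess larger. The 0.30 row would apply if the interim were run at 35 events and the trial ended near 117 (35/117 = 0.30). The figure of 117 comes from a log-rank event formula (see the fix), not from the plan.

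**The case against.** The strongest reply is that the discrepancy is trivial. The excess is 0.0013, the claim is given to two decimals, and 0.0513 rounds to 0.05. The calculation is also a large-sample approximation for a stratified log-rank test with about 35 events at the interim, so the true error is not known to four decimals. This stands as a comment on size. It does not rescue the boundary: group-sequential critical values are derived from the same approximation, the plan gives its own to three decimals, and on that basis they miss the target.

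Second, section 10.7 presents the procedure as guidance for decisions and refers to spending-function critical values, so recalculation at the actual fraction may be intended. It is not written, however. Fixed values are given, no spending function is specified, and section 10.8 makes 0.0492 the level of the final test.

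Third, the final p-values affected depend on the remedy chosen. The range is 0.0480 to 0.0492 under the classical boundary, and 0.0479 to 0.0492 if 2.782 is kept. Under the spending form it is only 0.0490 to 0.0492; there nearly all the excess comes from the interim threshold, since 2.963 with 1.967 gives 0.0502. This point is correct, and the wider window should not be read as applying to every remedy.

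Fourth, the 0.0526 figure rests on a final event count that the plan does not state. If the total were revised and the look kept at half of it, the error would again be 0.0513. It is a conditional scenario and the finding does not depend on it.

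**Conclusion.** The concern holds. On the plan's own inputs, the overall two-sided type I error is 0.0513 against a stated 0.05, an excess of 0.0013 (0.0013/0.05 = 2.6%). The result assumes looks at exactly 0.5 and 1.0 of the events, the usual large-sample joint normality of the log-rank statistics, and no binding futility rule; the documents contain none. Rounding does not explain it, and no standard O'Brien-Fleming version yields both values. The error is small and leaves design and conduct untouched, but it sits in the decision rule for the primary endpoint and should be corrected before the interim analysis.

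**What to change.** In section 10.7, name the boundary and state one consistent pair:

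- O'Brien-Fleming-type spending function, 0.025 per side: 2.963 and 1.969 (0.0031 and 0.0490). This fits the plan's description of the method as alpha spending.
- Classical O'Brien-Fleming: 2.797 and 1.977 (0.0052 and 0.0480).

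If the spending function is chosen, write out its formula and say that the critical values will be recomputed at the event fraction observed at each look, with the tabulated pair applying only at exactly 0.5. Replace 0.0492 with the chosen final level in sections 10.6 and 10.8.

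The cost is SAP wording. As a gauge of the effect on size, take the log-rank formula 4(z_α/2 + z_β)²/(ln HR)² with 85% power and HR = ln(1 − 0.114)/ln(1 − 0.19) = 0.574. Required events go from 117.4 at 0.0492 to 117.5 at 0.0490 or 118.2 at 0.0480, a change of less than one event. These counts differ from the plan's 70; that is a separate question and does not affect this correction.

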10.8 STATISTICAL ANALYSIS

The primary analysis will be an intent-to-treat analysis that will include all randomized participants regardless of treatment actually received or follow-up schedule.

Point Estimation and Interval Estimation: We will report maximum likelihood estimates for point estimation. For routine reporting, two-sided 95% confidence intervals for all parameters will be prepared.

Disposition of Participants and Baseline Comparisons: Summaries of all participants randomized and the number who complete visits at 30-days, and every 6 months after the day of randomization will be provided for each treatment group. The treatment groups will be compared at baseline with respect to demographics, baseline measurements related to efficacy and baseline measurements related to safety.

Univariate Analysis: All outcome measures will be described in a univariate analysis. For continuous variables means and standard deviations will be calculated. For discrete and dichotomous variables we will use contingency tables.

Analysis of Primary Endpoint: The primary endpoint of this study is defined time to first event requiring any ICD therapy (appropriate or inappropriate) or Incessant VT (VT occurring below the ICD rate cut-off); this will be assessed in the on-treatment patient cohort. An event requiring ICD therapy is defined as an anti-tachycardia pacing (ATP) or shock therapy. Time to event will be estimated using Kaplan-Meier curves. Survival time will be defined as the time (in months) between randomization and the occurrence of first ICD therapy. To compare the ICD+ RSDN arm with the ICD alone arm we will use a stratified log-rank statistic (using the stratification variables from the randomization procedure). A Cox proportional hazards model with treatment and other important prognostic factors as covariates will be used for the multivariate analysis of the times to first ICD therapy. Risk ratios and their 95% confidence intervals will be computed. Patients will be included in the analysis as censored if they are alive and free of ICD events at the end of the 18-month follow-up period. Although we do not anticipate interactions between treatment and stratification factors, formal tests for interactions will be assessed using proportional hazards models. A formal test of proportional hazards will assess the significance of

the interaction between the indicator for treatment group and log (t) in a Cox proportional hazards regression model that also includes the main effect for the randomization group. The final analysis will be based on a two tailed 0.0492 level test.

Analysis of Secondary End-points: All continuous variables will be analyzed using mixed effects models (Bagiella et al. 2000; Diggle et al. 1994; Laird and Ware 1982). Log-transformations will be used, if necessary to normalize the variables or stabilize the variance. For binary and discrete outcomes we will use generalized estimating equations (GEE) (Liang and Zeger 1986; Miller et al. 1993; Zeger and Liang 1986) to fit logistic or log-linear models that account for the dependency of the repeated measures.

Missing Data: For participants who withdraw consent to participate we will use all the information available up to the time of withdrawal. For the purpose of the primary analysis these patients will be censored at the time of withdrawal if they have not experienced the primary event. For all other variables, if the data are missing at random (MAR), that is, the probability of being missing depends only on observed values (Little and Rubin 1987), then likelihood-based methods such as mixed-effects models will be used for analysis without bias. If the fraction of missing data is small we expect that even non-ignorability can have only little effect on the final estimates. If the extent of missingness is large compared to the effect size, we will use the multiple imputation procedure proposed by Rubin (1997) and Little (1996).

